5. ANALYSIS POPULATIONS

The following subject populations will be used for analysis:

The Safety population will include all subjects who received at least one dose of study drug medication. Safety analysis will be performed on the Safety population.

The Intent-to-Treat (ITT) population will include all subjects who received at least one dose of study drug medication and had at least one post dose assessment. Efficacy, pharmacokinetic (PK) and pharmacodynamic (PD) analysis will be performed on the ITT population.

6. SUBJECT DISPOSITION

Subject disposition information will be summarized for all subjects by dose cohort. Summaries will include: the number of enrolled subjects, the number of subjects in each analysis population, the number of subjects who received both planned doses of VM202, the last scheduled visit completed, the number of subjects completing the study and the primary reason for discontinuation.

7. DEMOGRAPHIC AND BASELINE CHARACTERISTICS

Demographic variables include: age, sex, ethnicity, race. Medical history and peripheral vascular disease intervention history at baseline will also be considered. Demographic and baseline characteristics will be summarized for the Safety and ITT analysis populations.

8. EFFICACY ANALYSES

Efficacy analysis will be based on the ITT analysis population. The efficacy analysis generated for this study is intended to be used for preliminary and exploratory considerations and is not meant to be confirmatory in nature.

8.1 Efficacy Variables

The following efficacy endpoints of equal interest will be collected and analyzed:

- Area of Ischemic Ulcer (largest contiguous area of ulceration)
- Hemodynamic Assessments to include:
 - Ankle-Brachial Index (ABI)

- 2. Toe-Brachial Index (TBI)
- 3. Wave Form Analysis (PVR);
- Pain Visual Analogue Scale (VAS) Score;
- Transcutaneous Oxygen Pressure Assessment (TcPO₂);
- Subject Analgesic Use;
- High resolution MRA.

8.2 Baseline Values

The baseline value for each variable is the value recorded at the last visit on or before start of dosing. In most cases, baseline values are expected to be based on the assessment collected at the Day 1 (Pre-Dose) visit.

8.3 Handling Missing Data

Only data collected will be used for analysis. Missing values will not be imputed for this study.

8.4 Interim Analyses

No interim analysis of efficacy data is planned.

8.5 Multiplicity Adjustments

No alpha adjustments for multiple comparisons will be made since this is an open-label study with no formal cohort comparisons.

8.6 By Center Analyses

As this is a single center study, no by-center analysis is planned.

9. METHODS OF EFFICACY ANALYSIS

9.1 Area of Ischemic Ulcer

For each subject, the ulcer with the largest contiguous area will be measured both before and after the first dose of study medication. Planned post dose measurements of the ulcer include measurements at Day 15 (Pre-Dose), Day 28, Day 59, Day 91, Day 180 and Day 365. Ulcer measurements will be summarized using descriptive statistics at baseline and at each post baseline time point. Changes from baseline will also be summarized.

9.2 Hemodynamic Assessments

Hemodynamic assessments will be taken before the first dose of medication and at Day 15 (Pre-Dose), Day 28, Day 59, Day 91, Day 180 and Day 365. Hemodynamic assessments will be summarized using descriptive statistics at baseline and at each post baseline time point. Changes from baseline will also be summarized. Hemodynamic assessments, all in units of mmHg, include the following:

- Ankle Brachial-Index measurements taken on both legs. Counts and percentages
 of the index limb (right/left) will be also be presented;
- Toe Brachial-Index measurements taken on toe of right and left foot.

Confirmation that wave form analysis (PVR) was collected will be presented in listings.

9.3 Visual Analogue Scale for Pain

Throughout the study, subjects will be asked to assess the level of pain they feel by placing a perpendicular line on a scale of 0 (No Pain) to 100 (Pain as bad as it can be). The subject's Visual Analogue Scale (VAS) score will be determined by where the subject places the perpendicular line. Measurements of VAS will be collected prior to first study drug administration and at Day 15 (Pre-Dose), Day 28, Day 59, Day 91, Day 180 and Day 365 of the study. VAS measurements will be summarized using descriptive statistics at baseline and at each post baseline time point. Changes from baseline will also be summarized.

9.4 Transcutaneous Oxygen Pressure Assessment

Before the first dose of medication and at Day 15 (Pre-Dose), Day 28, Day 59, Day 91, Day 180 and Day 365 of the study, assessments of the transcutaneous oxygen pressure (TcPO₂) in various regions of the body will be taken. Those regions include assessments of the anterior calf, posterior calf, dorsum foot and chest. TcPO₂ measurements for each body region will be summarized using descriptive statistics at baseline and at each post baseline time point. Changes from baseline will also be summarized.

9.5 Subject Analgesic Use

Concomitant medication use will be collected throughout the study on an ongoing basis. A review of concomitant medications used by subjects will be carried out to determine which concomitant medications were administered for analgesic use. Based on the review of concomitant medications, subjects will be classified as either having used an analgesic or not. Counts and percentages showing the number of subjects having used or not having used analgesics will be presented.

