This Phase I study is designed to determine the safety and tolerability of intramuscular injections of VM202 using standard objective and subjective measurements. Assessment of safety will be accomplished through monitoring vital signs, monitoring signs and symptoms of acute and chronic hypersensitivity reaction and evaluating all observed and reported adverse events, retinal fundoscopy, clinical laboratory results, tumor lab testing, infection testing and urinalysis. There will also be a long-term follow-up to determine the extent of new onset of malignancy in treated subjects. CA-125 will be done in females and a PSA will be done in males to rule out any occult malignancy prior to first study drug administration and throughout the study.

While the primary objectives are safety and tolerability, preliminary efficacy evaluations will include evaluation of changes from Baseline in hemodynamics (ABI, TBI, Wave Form), TcPO₂, VAS pain assessment, analgesic use, and MRA measurements.

Procedures:

After the study subject is identified, a written informed consent will be obtained and screening process will be initiated. Hemodynamic assessments, TcPO₂, retinal fundoscopy and high resolution MRA will be done at Baseline. For subjects with

ischemic ulcer, a photograph and measurement of the ulcer will be obtained. Safety laboratory (hematology, chemistry, urinalysis), tumor marker tests, infection tests, chest X-ray or CT scan of the chest (if the subject has a previous history of tobacco use, a CT scan will be performed instead of the chest X-ray), and ECG will also be done at Baseline.

Subjects will be administered two doses of study drug on Days 1 and 15 as a local intra-muscular injection in the affected ischemic limb. There will be 4 or 8 injections depending on the dose level administered slowly for 20~30 seconds at predetermined sites on only one affected leg (mainly at the calf muscles) without local anesthesia. After treatment administration, subjects will be observed for 1 hour in a comfortable supine position.

Analgesic usage and Serum HGF will be assessed on Day 8 post first dose treatment.

After the second dose is administered (Day15) to the leg previously injected, hemodynamic assessments (ABI, TBI, Wave Form Analysis), TcPO₂, photograph and measurement of ischemic ulcer, VAS for pain, and safety labs will also be assessed on Days 28, 59, 91, 180 and 365. High resolution MRA with flow assessment will be done at Days 91 and 180.

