Descriptive statistics (N, mean, median, SD, minimum and maximum values, where applicable) of safety laboratory parameters to include tumor markers will be reported. Abnormalities will be summarized for low and high values. Frequency counts for normal/abnormal findings for retinal fundoscopy will be presented.

Efficacy:

Descriptive statistics (N, mean, median, SD, minimum and maximum values) of vascular assessments (ABI, TBI, Wave Form Analysis), TcPO₂, High resolution MRA, and VAS for pain will be reported. Frequency counts for analgesics use by dose cohort will be reported.

Pharmacokinetics:

Descriptive statistics (N, mean, median, SD, minimum and maximum values, where applicable) of VM202 DNA levels will be reported.

Pharmacodynamics:

Pharmacodynamics will assess change from Day 1 in anti-HGF antibodies and serum HGF levels at pre treatment and

endothelial progenitor cell assay post treatment between all 4-dose levels.

Sponsor:

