7.2.4 Subject Analgesic Use

Analgesic use including generic name, dose and frequency will be collected at Baseline and each subsequent visit and will be recorded on the CRF. Any change from in the dose level or frequency of analgesics used will be documented.

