9.3 Statistical Analysis

Safety and Tolerability:

The incidence and nature of adverse events will be reported in tabulated format. Adverse events will be described according to severity and to its relationship with the study drug. Serious adverse events and adverse events leading to treatment discontinuation will be listed.

Descriptive statistics (N, mean, median, SD, minimum and maximum values, where applicable) of safety laboratory parameters infection tests and tumor markers will be reported. Abnormalities will be summarized for low and high values.

Retinal fundoscopy results per treatment group will be reported as change from baseline and subsequent evaluation at day 365.

Efficacy:

Descriptive statistics (N, mean, median, SD, minimum and maximum values) of vascular assessments (ABI, TBI, Wave Form Analysis), TcPO₂, High Resolution MRA, VAS for pain, analgesic use, and ulcer size will be reported. Frequency counts for analgesics use by dose cohort will be reported.

Pharmacokinetics:

Descriptive statistics (N, mean, median, SD, minimum and maximum values, where applicable) of VM202 DNA levels will be reported.

Pharmacodynamics:

Descriptive statistics (N, mean, median, SD, minimum and maximum values, where applicable) of endothelial progenitor cell assay levels, anti-HGF antibody levels and serum HGF levels will be reported.

Change in endothelial progenitor cell levels from Baseline will be described for each treatment dose at each selected time point.

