10.10 Prior and Concomitant Medications

Verbatim terms on case report forms will be mapped to Anatomical/Therapeutic/Chemical (ATC) Level 4 categories and Drug Reference Names using the World Heath Organization (WHO) dictionary (version 5.3).

Prior medications are those medications taken within 30 days prior to the initial dose of study drug. Concomitant medications are those medications taken after the initial dose of study drug. Prior and concomitant medications will be summarized for each treatment by

WHO ATC class and medication name. These summaries will present the number and percentage of subjects using each medication. Subjects may have more than one medication per ATC category and medication. At each level of subject summarization, a subject is counted once if he/she reported one or more medications at that level. Each summary will be ordered by descending order of incidence of ATC class and medication within each ATC class.

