Programmer Note For each measurement, repeat for all available time points. Results for other measurements to be shown include Dosrum Foot and Chest..

^[2] Change= Change from Baseline

Protocol Number: US-06-1-001

Table 10 Subject Analgesic Use [1] ITT Population

| | VM202- 2 mg (N=) | VM202- 4 mg (N=) | VM202- 8 mg (N=) | VM202- 16 mg (N=) |
|------------------------------------|----------------------|----------------------|----------------------|-----------------------|
| Subject reported using analgesic d | uring study? | | | |
| Yes | n (%) | n (%) | n (%) | n (%) |
| No | n (%) | n (%) | n (%) | n (%) |

[1] Subject identified as having used analgesic based on whether subject reported using any concomitant medications considered to be an analgesic.

path\t_program.sas date time

Programmer Note:

Table 11 Study Drug Exposure Safety Population

| | VM202- 2 mg | VM202- 4 mg | VM202-8 mg | VM202- 16 mg |
|---|--------------|--------------|--------------|--------------|
| | (N=) | (N=) | (N=) | (N=) |
| | | | | |
| Day 1 Dose Administered? | | | | |
| | - (0/) | - (0/) | - (0/) | - (0/) |
| Yes | n (%) | n (%) | n (%) | n (%) |
| No, DLT from previous injection | n (%) | n (%) | n (%) | n (%) |
| No, Other | n (%) | n (%) | n (%) | n (%) |
| Zone of Injections | | | | |
| I | n (%) | n (%) | n (%) | n (%) |
| П | n (%) | n (%) | n (%) | n (%) |
| Ш | n (%) | n (%) | n (%) | n (%) |
| IV | n (%) | n (%) | n (%) | n (%) |
| V | n (%) | n (%) | n (%) | n (%) |
| VI | n (%) | n (%) | n (%) | n (%) |
| Total Volume Administered per Protocol? | | | | |
| Yes | n (%) | n (%) | n (%) | n (%) |
| No | n (%) | n (%) | n (%) | n (%) |
| Time Dose Administration (mg) | | | | |
| N | n | n | n | n |
| Mean (SD) | xx.x (xx.xx) | xx.x (xx.xx) | xx.x (xx.xx) | xx.x (xx.xx) |
| Median | XX.X | XX.X | xx.x | XX.X |
| Min, Max | xx, xx | xx, xx | xx, xx | xx, xx |
| Day 15 | | | | |
| Dose Administered? | | | | |
| Yes | n (%) | n (%) | n (%) | n (%) |
| No | n (%) | n (%) | n (%) | n (%) |
| 110 | 11 (70) | 11 (70) | 11 (70) | 11 (70) |
| | | | | |

Page 1 of x

Viromed Co., Ltd. Protocol Number: US-06-1-001

Table 12 Treatment Emergent Adverse Events by Cohort [1] Safety Population

| | VM202- 2 mg (N=) | | VM202- 4 mg (N=) | | VM202-8 | mg (N=) | VM202-16 mg (N=) | |
|---|-------------------|-----------|-------------------|-----------|--------------|-----------|-------------------|-----------|

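### SAP 9.5 and Table 10 give analgesic use as one whole-study Yes/No, so the tables cannot show whether a pain VAS change came with more or less analgesia

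*SAP*

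**What the plan says.** **Protocol.** The Rationale in the synopsis describes the preliminary efficacy work as "evaluation of changes from Baseline in hemodynamics (ABI, TBI, Wave Form), TcPO₂, VAS pain assessment, analgesic use, and MRA measurements". Section 7.2.4 sets the data collection: "Analgesic use including generic name, dose and frequency will be collected at Baseline and each subsequent visit". It adds: "Any change from in the dose level or frequency of analgesics used will be documented". Section 9.3 puts analgesic use in its list of variables for descriptive statistics ("VAS for pain, analgesic use, and ulcer size will be reported") and then adds a second output, which the synopsis also carries: "Frequency counts for analgesics use by dose cohort will be reported".

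**SAP.** Section 9.5 has a reviewer pick out the analgesics from the concomitant medications and then makes one classification: "Based on the review of concomitant medications, subjects will be classified as either having used an analgesic or not". Counts and percentages follow. The Table 10 shell in Appendix B has a Yes row and a No row for each dose cohort and nothing else. Its footnote reads: "Subject identified as having used analgesic based on whether subject reported using any concomitant medications considered to be an analgesic". By contrast, SAP 9.3 and Table 8 summarise pain VAS at baseline, at each later time point and as change from baseline.

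**The concern.** Pain VAS is read here as a before-after change with no control group, in cohorts of 3. A lower score means one thing if the subject has cut back on analgesics and another if the subject has added them. The protocol leaves room for both. Its definition of critical limb ischemia in section 5.2 counts pain medication as part of the standard therapy on which symptoms are stable, and section 6.4.1 bars no medication other than investigational products. Section 5.2 asks subjects to maintain their arterial disease therapy and names antiplatelet and statin treatment; it does not name analgesics.

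A flag that turns to Yes at the first analgesic and stays there cannot separate these cases. What is at stake is whether the preliminary pain result can be interpreted from the tables.

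**Working it through.** The documents state no sample size, power or error rate for this measure, so there is no planned figure to reproduce. The check compares the provisions and counts the schedule.

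**1. Provision against output**

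| Protocol provision | What Table 10 gives |
|---|---|
| Synopsis, Rationale: change from Baseline | Nothing |
| 7.2.4: drug, dose and frequency at Baseline and each visit, with changes documented | One flag; any analgesic at any dose is Yes |
| 9.3: descriptive statistics | Nothing |
| Synopsis and 9.3: frequency counts by cohort | Delivered |

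**2. Is a paired summary feasible?** From Table 4-1:
- Analgesic use: Screening, Day 1 pre-dose, Days 8, 15 (pre-dose), 16, 21, 28, 59, 91, 180 and 365. That is 2 pre-dose + 9 post-dose = 11 points.
- Pain VAS: Screening, Day 1 pre-dose, Days 15 (pre-dose), 28, 59, 91, 180 and 365. That is 2 pre-dose + 6 post-dose = 8 points.
- All 8 VAS points are also analgesic points. So 6 of 6 scheduled post-dose VAS changes can be paired with an analgesic change; Tables 8 and 10 pair 0 of 6.

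**3. What the flag hides.** The doses here are assumed, for illustration only. Take three cohorts of 3, every subject starting at 4 units a day.

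| Path | Day 15 | Day 28 | Day 59 | Day 91 | Day 180 | Day 365 | Change at Day 365 | Table 10 |
|---|---|---|---|---|---|---|---|---|
| Stable | 4 | 4 | 4 | 4 | 4 | 4 | 4 − 4 = 0 | 3/3 Yes |
| Stopped | 4 | 2 | 1 | 0 | 0 | 0 | 0 − 4 = −4 | 3/3 Yes |
| Doubled | 4 | 6 | 7 | 8 | 8 | 8 | 8 − 4 = +4 | 3/3 Yes |

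The three entries are identical. This follows from the rule itself and needs no assumption about how common analgesic use is.

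**4. Do other planned outputs fill the gap?** Table 24 counts users by drug class and drug, again over the whole study. SAP 10.10 says prior medications will be summarised too, although Appendix A lists no such table. If produced, it would count users in the 30 days before dosing, without dose, frequency or change. Listings 11 (VAS), 13 (analgesics) and 25 (all concomitant medications) hold subject-level records, but they are separate and their columns are not specified.

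**5. Which period does the flag cover?** SAP 10.10 says: "Concomitant medications are those medications taken after the initial dose of study drug". If that definition governs 9.5, the flag is post-dose only. But 9.5 and the Table 10 shell refer to the study as a whole, and Table 4-1 records concomitant medications from Screening. The window is therefore not settled. On either reading there is still only one flag per subject.

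**The case against.** The strongest reply is that this is a minor presentation matter. Analgesic use is not among the protocol's listed secondary efficacy endpoints, which are hemodynamics with TcPO₂, VAS and ulcer area. The synopsis paragraph on efficacy evaluation omits it, and the synopsis statistics ask only for the frequency count that Table 10 supplies. Protocol 9.1 plans no statistical analysis of efficacy, and SAP 8 calls the efficacy work exploratory. With 12 to 15 subjects, a reader can go to the listings. Table 10 is not alone either: wave form and MRA also get listings only.

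Most of this stands, and it limits the weight of the point. It does not close the gap. The Rationale, 7.2.4 and 9.3 together ask for more than a frequency count. Description is the only efficacy output planned, so it should be readable, and matching separate listings by hand is a poor substitute.

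A further objection also stands: cohort counts of increased and decreased use, set beside mean VAS change, are two marginal summaries and do not show which subject's VAS fell with more analgesia. The fix therefore needs a subject-level display.

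A reader might also infer that nearly every subject would be a Yes, which would make the table empty of information. The documents give no rate of use, and entry is possible with ischemic ulcers without rest pain, so that cannot be asserted.

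**Conclusion.** The point holds as a gap in the descriptive plan. Table 10 meets one of the two outputs in protocol 9.3 and does not carry the change from Baseline named in the synopsis. As planned, none of the 6 scheduled post-dose VAS changes can be read against analgesic change from the tables.

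Three stronger readings are not supported:
- The SAP has not dropped a listed endpoint; analgesic use is not on that list.
- The flag is not shown to be post-dose only; that depends on carrying the SAP 10.10 definition into 9.5.
- No test or error rate is wrong, and safety conclusions, dose escalation and the MTD are not affected.

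The conclusion rests on the text and the table shells. The dose paths above only illustrate it. The CRF is not available, so the recorded detail could not be checked.

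**What to change.** 1. **State the window in SAP 9.5**: whether the classification covers use before the first dose, after it, or both.
2. **Replace Table 10** with analgesic use, n (%), at Baseline (as in SAP 8.2) and at each scheduled visit by cohort, plus a change category against Baseline:
   - increased: a drug added, or a higher dose or frequency of the same drug, with nothing stopped or lowered;
   - decreased: a drug stopped, or a lower dose or frequency of the same drug, with nothing added or raised;
   - unchanged;
   - not classifiable: switches and mixed changes that the rule does not settle.

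   Write the coding rule before the analysis. In line with SAP 8.3, leave a subject without a record out of that visit and show the number observed.
3. **Show the pairing by subject**: print each subject's change category next to that subject's VAS change at Days 15, 28, 59, 91, 180 and 365, for example by merging Listings 11 and 13.

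**Cost.** One replaced shell, one merged listing and a short coding rule. Protocol 7.2.4 already requires the data, but the CRF pages must be checked for dose, frequency and dates. Cells will be sparse with 3 subjects per cohort, and drug switches need some judgement. Table 4-1 schedules VAS but no analgesic-use item at Early Termination; concomitant medications are recorded there, so pairing at that visit would depend on what that record holds.

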9.6 High Resolution MRA

Occluded arteries will be identified as one of the following categories on CRFs: Super femoral artery (SFA), popliteal, peroneal, anterior tibeal, post tibial, infrapopliteal. Information regarding occluded arteries will be presented in listings. The quantitative blood flow of the target occluded artery and the volumetric analysis of newly developed artery will be not be recorded on the CRF. That information will be in a separate report compiled by the site and another vendor.

10. SAFETY ANALYSES

All subjects who received study drug will be included in the safety analyses, analyzed according to the study treatment actually received.

10.1 Study Drug Exposure

Study drug exposure will be summarized by dose cohort for Day 1 (planned first dose of VM202) and Day 15 (planned second dose of VM202). Categorical variables to be summarized using counts and percentages include "Was dose administered?" (Yes, No), the zone of the dose administration (I, II, III, IV, V, VI) and "Was the total volume of dose administered per protocol?" (Yes, No). In addition, the volume of study drug administered (continuous variable) will be summarized in minutes using summary statistics.

